### 7.6.2 Definition of Treatment-Emergent Adverse Event

A TEAE is any condition that was not present prior to treatment with the study product but appeared following treatment, was present at treatment initiation but worsened during treatment, or was present at treatment initiation but resolved and then reappeared while the individual was on treatment (regardless of the intensity of the AE when the treatment was initiated).

### 7.6.3 Definition of Serious Adverse Event

A serious adverse event or reaction is any untoward medical occurrence that, at any dose has any of the following consequences:

- Results in death
- Is life-threatening
- Requires in-patient hospitalization or prolongation of existing hospitalization
- Results in persistent or significant disability/incapacity
- Is a congenital anomaly/birth defect

Note: The term “life-threatening” in the definition of “serious” refers to an event in which the subject was at risk of death at the time of the event; it does not refer to an event that hypothetically might have caused death if it were more severe.

Medical and scientific judgment should be exercised in deciding whether expedited reporting is appropriate in other situations, such as important medical events that may not be immediately life-threatening or result in death or hospitalization, but may jeopardize the subject or may require intervention to prevent one of the other outcomes listed in the definition above. These should also usually be considered serious.

Examples of such events are intensive treatment in an emergency room or at home for allergic bronchospasm, blood dyscrasias, or convulsions that do not result in hospitalization; or development of drug dependency or drug abuse.

## 7.6.4 Classification of an Adverse Event

### 7.6.4.1 Relationship to Study Product

The investigator will establish causality of the AE to the experimental treatment. The investigator should take into account the subject's history, most recent physical examination findings, and concomitant medications.

The degree of “relatedness” of the AE to the study medication must be described using the following scale:

**Not related** indicates that there is not a reasonable possibility for relationship of the event to the study medication.

**Possibly related** indicates that a direct cause and effect relationship between study medication and the AE has not been demonstrated, but there is evidence to suggest there is a reasonable possibility that the event was caused by the study medication.

**Probably related** indicates that there is evidence suggesting a direct cause and effect relationship between the AE and the study medication.

The statement "**reasonable possibility for relationship**" meaning that there are facts (e.g., evidence such as de-challenge/re-challenge/temporal relationship, exposure, likely cause due to known safety profile etc) to suggest a positive causal relationship. The investigators may also change their opinion for causality after follow-up information and may provide a follow-up SAE report with the revised causality assessment.

### 7.6.4.2 Adverse Event Severity

The intensity of an AE is an estimate of the relative severity of the event made by the investigator based on his or her clinical experience and familiarity with the literature. The following definitions are to be used to rate the severity of an AE:

- **Mild:** The symptom is barely noticeable to the subject and does not influence performance of daily activities. Treatment is not ordinarily indicated.
- **Moderate:** The symptom is sufficiently severe to make the subject uncomfortable, and performance of daily activities is influenced. Treatment may be necessary.
- **Severe:** The symptom causes severe discomfort, and daily activities are significantly impaired or prevented. Treatment may be necessary.

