#### **4.4.1 Interruption criteria**

A subject who meets either of the below criteria will have the study drug interrupted until laboratory retesting is performed and/or event resolution.

- neutrophils  $> 0.5 \times 10^3 / \mu\text{L}$  but  $< 1 \times 10^3 / \mu\text{L}$ ;
- platelet count  $> 50 \times 10^3 / \mu\text{L}$  but  $< 100 \times 10^3 / \mu\text{L}$ ;
- lymphocytes  $< 0.5 \times 10^3 / \mu\text{L}$  but  $> 0.2 \times 10^3 / \mu\text{L}$ ;
- CPK  $> 10 \times \text{ULN}$ ;
- an infection requiring IV treatment with antiviral, antibiotic, antiprotozoal, antiparasite or requiring oral medications of those longer than 2 weeks;
- AST/ALT  $> 5 \times \text{ULN}^*$ .

\*Decision to restart the medication following any laboratory abnormality described above will be made in consultation with the study sponsor and medical monitor.

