#### **4.4.2 Permanent study discontinuation**

Adverse events or laboratory abnormalities who meet either of the below criteria will result in permanent study discontinuation of the subject. Treatment with the study product will be immediately stopped and the subject withdrawn from this study.

- serious opportunistic infection such as tuberculosis;
- hypertension that cannot be controlled with additional antihypertensive medication(s);
- neutrophils  $\leq 0.5 \times 10^3 / \mu\text{L}$ ;
- lymphocytes  $\leq 0.2 \times 10^3 / \mu\text{L}$ ;
- platelets  $\leq 50 \times 10^3 / \mu\text{L}$ ;
- diagnosis of malignancy;
- venous thrombo-embolic event or major cardiovascular event.

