15. Subject has positive results for hepatitis B surface antigens (HBsAg), antibodies to hepatitis B core antigens (anti-HBc), hepatitis C virus (HCV), or human immunodeficiency virus (HIV) at the screening visit.
16. Presence of any of the following laboratory abnormalities at the screening visit:
  - a. Hemoglobin  $< 11$  g/dL;
  - b. White blood cell (WBC)  $< 3.0 \times 10^3$  / $\mu$ L;
  - c. Platelet count  $< 125 \times 10^3$  / $\mu$ L;
  - d. Neutrophils  $< 1.8 \times 10^3$  / $\mu$ L;
  - e. Lymphocytes  $< 1.0 \times 10^3$  / $\mu$ L;
  - f. Aspartate aminotransferase (AST)/alanine aminotransferase (ALT)  $> 2 \times$  the upper limit of normal (ULN).
  - g. Total bilirubin  $> 1.2 \times$  ULN (except for elevated indirect bilirubin secondary to Gilbert's syndrome);
  - h. Creatinine  $>$  ULN.
17. Subjects has uncontrolled hypertension within the last 1 month prior to screening or blood pressure at screening of systolic blood pressure  $> 160$  mm Hg or diastolic BP  $> 95$  mm Hg, confirmed by one repeat assessment.
18. Subject has a known active tuberculosis or a positive tuberculosis (TB) infection test. Subject will be evaluated for latent TB infection with a purified protein derivative (PPD) test or a QuantiFERON-TB Gold test. Subjects who demonstrate evidence of latent TB infection (either PPD  $\geq 5$  mm of induration or positive QuantiFERON-TB Gold test, irrespective of bacille Calmette-Guérin vaccination status) will only be allowed to participate in the study if there is documented evidence of a completed adequate treatment course for latent TB (with negative chest x-ray findings for active TB).
19. Subject has difficulty swallowing medications, or known history of malabsorption syndrome.
20. Subject has a history of recurrent gastroesophageal reflux disease (GERD) requiring the use of proton pump inhibitors within the last month.

21. Subject has a known history of diverticulitis.
22. Subject has uncontrolled diabetes.
23. Any medical or psychiatric condition which, in the opinion of the investigator or the sponsor's medical monitor, would place the subject at risk, interfere with participation in the study, or interfere with the interpretation of study results.
24. Subject has used dupilumab within 12 weeks prior to Day 1.
25. Subject has received any UV-B phototherapy (including tanning beds) or excimer laser within 4 weeks prior to Day 1.
26. Subject has had psoralen-UV-A (PUVA) treatment within 4 weeks prior to Day 1.

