If deemed appropriate by the investigator, clinically significant findings in clinical laboratory testing will exclude a subject from study participation. Any significant change will be reported as an AE.

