## 7.6 Adverse Events and Serious Adverse Events

### 7.6.1 Definition of Adverse Event

An AE is any untoward medical occurrence in a subject administered a pharmaceutical product and that does not necessarily have a causal relationship with this treatment. An AE can therefore be any unfavorable and unintended sign (including an abnormal laboratory finding), symptom, or disease temporally associated with the use of a study product, whether or not considered related to the study product. AEs and SAEs will be collected from the time of informed consent signature until the final visit / contact.

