## 7.6.5 Time Period and Frequency for Event Assessment and Follow-Up

The occurrence of an AE or SAE may come to the attention of study personnel during study visits and interviews of a study subject presenting for medical care, or upon review by a study monitor.

All AEs, including local and systemic reactions, will be captured on the appropriate eCRF. Information to be collected includes event description, date of onset, clinician's assessment of severity, relationship to study product (assessed only by those with the training and authority to make a diagnosis), and date of resolution/stabilization of the event. All AEs occurring while on study must be documented appropriately regardless of relationship.

Before subject enrollment, study site personnel will note the occurrence and nature of each subject's medical condition(s) in the appropriate section of the source document and eCRF. During the study, site personnel will note any change in the condition(s) and the occurrence and nature of any AE.

Any medical condition that is present at the time of consent signature will be considered as part of medical history and not reported as an AE. However, if the study subject's condition deteriorates after the consent signature, it will be recorded as an AE.

If a subject experiences an AE at any time after the informed consent signature until the end of participation in the study, the event will be recorded as an AE in the source document and eCRF. Any SAE related to the study participation (e.g., screening procedure) will be recorded in the source document and eCRF from the time a subject consents to participate in the study until the end of participation in the study.

The investigator is responsible for appropriate medical care of subjects during the study. The investigator also remains responsible for following through with an appropriate health care option for all AEs that are ongoing at the end of the study. The subject should be followed until the event is resolved or stable. If an AE is ongoing at the end of study, the follow-up duration is left to the discretion of the investigator. Follow-up frequency will be performed at the discretion of the investigator.

Whenever possible, clinically significant abnormal laboratory results are to be reported using the diagnostic that resulted in the clinically significant abnormal laboratory results and not the actual abnormal test.

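### No by-arm haematology or chemistry table named in the SAP counts subjects reaching the protocol's interruption or stopping values, and SAP 5.7 can drop those values from the summaries

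*Protocol*

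**What the plan says.** **Action values.** Protocol 4.4.1 sets interruption ranges for neutrophils (above 0.5, below 1), platelets (above 50, below 100) and lymphocytes (above 0.2, below 0.5), all x10^3/uL, and limits for CPK (above 10 x ULN) and AST/ALT (above 5 x ULN). Its rule is: "A subject who meets either of the below criteria will have the study drug interrupted until laboratory retesting is performed and/or event resolution". Protocol 4.4.2 sets stopping values: neutrophils at or below 0.5, lymphocytes at or below 0.2, platelets at or below 50. There, "Treatment with the study product will be immediately stopped and the subject withdrawn from this study".

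**Laboratory changes as AEs.** Protocol 7.3.4 says "Any significant change will be reported as an AE". Protocol 7.6.5 prefers the underlying cause: "Whenever possible, clinically significant abnormal laboratory results are to be reported using the diagnostic" behind them. Under 7.6.4.2, severity is an investigator's estimate "based on his or her clinical experience and familiarity with the literature", with three levels worded around a symptom and daily activities. Moderate, for example, reads: "The symptom is sufficiently severe to make the subject uncomfortable, and performance of daily activities is influenced".

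**Tables.** SAP 13.1 names an overall AE table with rows for TEAEs leading to interruption and to discontinuation, TEAEs by SOC, PT and severity, and the TEAEs of clinical relevance or interest by SOC and PT. SAP 13.2 names descriptive statistics, change from baseline, shift tables to abnormality, frequencies of qualitative urinalysis results, and listings.

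**Data rules.** SAP 5.7 takes the repeat result into the summary when a retest is done. It lists unscheduled safety values but keeps them out of by-visit tables, and it summarises ET as a separate visit. Protocol Table 1 schedules post-baseline laboratory draws at Week 4, Week 12 and follow-up/ET.

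**The concern.** Safety and tolerability is a secondary objective of this three-dose trial. Of the 12 TEAEs singled out in SAP 13.1, five are laboratory-defined: neutropenia, lymphopenia, eosinopenia, CPK elevation and anemia. A reader weighing 40, 60 and 80 mg would want to know how many subjects per arm reached the values at which the protocol itself acts, and on which parameter. No named table gives that count.

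The deepest values are also the ones most likely to be rechecked or to be found at unscheduled visits. The retest and unscheduled-value rules can therefore remove from the laboratory summaries the results that led to action.

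**Working it through.** **1. Limits to count against.** Neutrophils, lymphocytes and platelets have two each; CPK, AST and ALT have one each. 3 x 2 + 3 x 1 = 9 limits over 6 parameters.

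**2. Named by-arm outputs against those limits.**

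| Output | What it counts | Subjects per limit and parameter? |
|---|---|---|
| Overall AE table | TEAEs leading to interruption or discontinuation, all causes | No |
| TEAE by SOC/PT/severity | Investigator's rating under 7.6.4.2 | No |
| TEAEs of relevance/interest | SOC and PT, no severity | No |
| Descriptive statistics | n, mean, SD, median, minimum, maximum | No; the extreme shows one value |
| Shift tables | Shift to abnormality | None named |

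Qualitative urinalysis frequencies lie outside these parameters, so the point is confined to haematology and chemistry.

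**3. Effect of the retest rule (all values assumed).** One arm of 55; k subjects have neutrophils of 0.7 at Week 4, the others 4.0; rechecks lie between 1.2 and 2.5.

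- Recheck treated as unscheduled: mean = ((55 - k) x 4.0 + k x 0.7)/55.
- Recheck treated as a retest: replace 0.7 by the recheck value.

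| k | Mean, unscheduled | Mean, retest (1.2 to 2.5) | Minimum | Summarised count below 1.0 |
|---|---|---|---|---|
| 1 | 3.94 | 3.95 to 3.97 | 0.7, becoming 1.2 to 2.5 | 1, becoming 0 |
| 3 | 3.82 | 3.85 to 3.92 | 0.7, becoming 1.2 to 2.5 | 3, becoming 0 |
| 6 | 3.64 | 3.70 to 3.84 | 0.7, becoming 1.2 to 2.5 | 6, becoming 0 |

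The mean moves little. The minimum and the number of summarised values below 1.0 change outright, and a recheck within the normal range also removes the shift. A low value found at an unscheduled visit between Week 4 and Week 12 (84 - 28 = 56 days) stays out of by-visit tables.

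**4. What the overall AE table recovers (all values assumed, no retests).** Two arms of 55, each with 47 subjects at 4.0 and 8 with low neutrophils, taking 1.5 as below normal and assuming a single low category. Arm 1: all 8 at 1.5. Arm 2: 4 at 1.5, 3 at 0.8, 1 at 0.4.

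- Shift counts 8 and 8; medians 4.0 and 4.0.
- Means (47 x 4.0 + 8 x 1.5)/55 = 3.64 and (47 x 4.0 + 4 x 1.5 + 3 x 0.8 + 0.4)/55 = 3.58.
- SDs 0.89 and 1.04; minima 1.5 and 0.4.
- Overall AE table, if 4.4 is followed and each change is reported as a TEAE: 0 and 3 added to the interruption row, 0 and 1 to the discontinuation rows.

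Those rows separate the arms but do not name the cause. Three infections meeting 4.4.1 would add the same 3/55 = 5.5%. A table by parameter would show 0 and 4 below 1.0, of which 0 and 1 at or below 0.5.

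**The case against.** **By-arm information exists.** Action under 4.4 is mandatory, so the overall AE table should count most affected subjects by arm, and discontinuations are also listed. This stands: it would be wrong to infer that everything must be counted by hand from listings. What those rows lack is the parameter.

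**Layouts are held elsewhere.** SAP 5 places table formats in a separate document, and 13.2 does not say how many categories a shift table has. This stands too. The point covers only what the SAP names, and no count of collapsed categories should be read into it.

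**The retest rule may be aimed elsewhere.** Protocol 5.4 and 7.3.4 also speak of repeating a screening test. But SAP 5.7 is not limited to screening, and 4.4.1 uses the word retesting for the recheck after interruption. The natural reading therefore includes that recheck, though the SAP does not settle it.

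**Nothing promised is missing.** Protocol 8.3.3 commits to descriptive values and change from baseline, without safety inference, and SAP 13.2 adds to that. The Phase 1b summary in 2.1.2 reports no clinically significant laboratory changes, so counts may be low. Both are fair and keep the point small.

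**Severity wording.** A reader might infer that 7.6.4.2 is defective for laboratory AEs. The documents do not support that. It is a functional intensity scale, supplemented by investigator judgement and a treatment clause, and is not presented as laboratory grading. It follows only that the severity table cannot stand in for a count by measured value.

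**Conclusion.** The point holds for haematology and chemistry. None of the by-arm tables named in the SAP counts subjects against any of the 9 limits by parameter. Under SAP 5.7, read naturally, the value that triggered an interruption can be missing from means, minima and shift tables. That goes beyond missing detail, but it is a modest improvement to consider: it touches only the descriptive safety summary and leaves efficacy and type I error alone.

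The size in this trial cannot be known from the documents. The neutrophil figures are assumed and show the mechanism only. The retest part depends on how a recheck after interruption is classified; the absence of a count by parameter does not.

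A reader might also infer that subjects are less well protected or that the values are lost. Neither follows. The rules in 4.4 act on individual results, the DSMB reviews unblinded safety data by arm at least three times, and retest and unscheduled values are listed.

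**What to change.** Before unblinding, add to SAP 13.2 one by-arm table of each subject's worst on-treatment value.

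- **Values used:** scheduled, unscheduled and original (pre-retest).
- **Window:** from after the first dose to the last dose of study product plus a short fixed period set by the sponsor. It must take in the Week 12 draw for subjects still on drug (no dose is given at that visit) and the ET draw at discontinuation. It must exclude later off-drug draws, such as those of subjects who stop product for oral corticosteroids under Protocol 6.4.2 item 4 but attend to Week 12.
- **Counts:** neutrophils <1.0 and <=0.5; lymphocytes <0.5 and <=0.2; platelets <100 and <=50 (all x10^3/uL); CPK >10 x ULN; AST and ALT separately, >5 x ULN.
- **Optional:** haemoglobin <11 g/dL, from exclusion criterion 16a in 5.2. Add no eosinophil cut-off or lower haemoglobin cut-off, since the documents give no source for one.

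Leave 7.6.4.2 and the investigators' ratings unchanged. The cost is one derivation and one table from data already collected and listed, with no protocol amendment or site retraining. The downside is small counts per band.

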### 7.6.4.3 Expectedness

The expectedness of each SAE in relation to the study product will be determined, in consultation with the Sponsor when necessary.

## 7.6.5 Time Period and Frequency for Event Assessment and Follow-Up

The occurrence of an AE or SAE may come to the attention of study personnel during study visits and interviews of a study subject presenting for medical care, or upon review by a study monitor.

All AEs, including local and systemic reactions, will be captured on the appropriate eCRF. Information to be collected includes event description, date of onset, clinician's assessment of severity, relationship to study product (assessed only by those with the training and authority to make a diagnosis), and date of resolution/stabilization of the event. All AEs occurring while on study must be documented appropriately regardless of relationship.

Before subject enrollment, study site personnel will note the occurrence and nature of each subject's medical condition(s) in the appropriate section of the source document and eCRF. During the study, site personnel will note any change in the condition(s) and the occurrence and nature of any AE.

Any medical condition that is present at the time of consent signature will be considered as part of medical history and not reported as an AE. However, if the study subject's condition deteriorates after the consent signature, it will be recorded as an AE.

If a subject experiences an AE at any time after the informed consent signature until the end of participation in the study, the event will be recorded as an AE in the source document and eCRF. Any SAE related to the study participation (e.g., screening procedure) will be recorded in the source document and eCRF from the time a subject consents to participate in the study until the end of participation in the study.

The investigator is responsible for appropriate medical care of subjects during the study. The investigator also remains responsible for following through with an appropriate health care option for all AEs that are ongoing at the end of the study. The subject should be followed until the event is resolved or stable. If an AE is ongoing at the end of study, the follow-up duration is left to the discretion of the investigator. Follow-up frequency will be performed at the discretion of the investigator.

Whenever possible, clinically significant abnormal laboratory results are to be reported using the diagnostic that resulted in the clinically significant abnormal laboratory results and not the actual abnormal test.

Worsening of atopic dermatitis is captured by efficacy assessments and will not be recorded as an AE.

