### 7.6.7 Serious Adverse Events Reporting

[REDACTED] will be responsible for the overall pharmacovigilance process for this study. All SAEs, related to the experimental treatment or not, occurring during the course of the study must be reported on an SAE form to [REDACTED] (see below) within 24 hours of the knowledge of the occurrence (this refers to any AE that meets one or more of the aforementioned serious criteria). The SAE reporting period ends at the end of the follow-up period or if the subject begins an alternative therapy.

Reporting should be done by sending the completed SAE form to the following e-mail address (faxing can also be done as a second option in case e-mailing is not possible).

Safety Contact Information: **PPD**

E-mail: **PPD**

Fax: **PPD**

[REDACTED] will inform the sponsor, primary medical monitor, and CRO within 1 business day of awareness of a new SAE. [REDACTED] will process and evaluate all SAEs as soon as the reports are received. For each SAE received, [REDACTED] will make a determination as to whether the criteria for expedited reporting to relevant regulatory authorities have been met. [REDACTED] will manage the AE reporting, including suspected unexpected serious adverse reactions, in accordance with the applicable local regulations. SAEs will be reported to the IRB/EC as per local IRB/EC requirements.

The study sponsor will be responsible for notifying the Food and Drug Administration (FDA) of any unexpected fatal or life-threatening suspected adverse reactions as soon as possible, but in no case later than 7 calendar days after the sponsor's initial receipt of the information. In addition, the sponsor must notify the FDA and all participating investigators in an Investigational New Drug (IND) safety report of potential serious risks, from clinical trials or any other source, as soon as possible, but in no case later than 15 calendar days after the sponsor determines that the information qualifies for reporting.

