### **8.3.3 Safety Analyses**

All safety data, including AEs and SAEs will be presented and tabulated according to Medical Dictionary for Regulatory Activities (MedDRA) classification. Descriptions of AEs will include the start date, the stop date (if it resolved), the severity and seriousness of the AE, the causality of the AE to study product, and the outcome. The focus in this protocol will be the prevalence of TEAEs and drug-related TEAEs.

Reported AEs will be summarized by the number of subjects reporting the events, as well as by System Organ Class, Preferred Term, severity, seriousness, and relationship to study product. For the summary of AEs by severity, each subject will be counted only once within a System Organ Class or a Preferred Term by using the AEs with the highest intensity within each category for each analysis. For the summary of AEs by relationship to study product, each subject will be counted only once within a System Organ Class or a Preferred Term by using the AEs with the greatest reported relationship within each category. For the summary of AEs by relationship to study product and severity, each subject will be counted only once within a System Organ Class or a Preferred Term by using (1) the greatest reported relationship followed by (2) the highest reported intensity.

All information pertaining to AEs noted during the study will be listed by subject, detailing verbatim, System Organ Class, Preferred Term, start date, stop date, intensity, outcome, and relationship to study product. The AE onset will also be shown relative (in number of days) to the day of study product administration. SAEs will be tabulated by treatment group, relationship to the test article, and a reference to the occurrence of the SAEs to the relative day of dosing.

Results from laboratory analyses, vital signs, ECGs, and physical examinations will be tabulated by treatment and visit using descriptive statistics. The value at each visit as well as the change from baseline will be presented descriptively.

Concomitant medications will be coded with the World Health Organization (WHO) Drug Dictionary and listed by subject. Summary of medication classes will also be tabulated.

No inferential statistics will be done on safety variables.

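### The protocol bars recording worsening atopic dermatitis as an AE, yet its SAE definition covers a serious flare; no precedence is stated, so serious flares may go unreported or be handled differently by site.

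*Protocol*

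**What the plan says.** Protocol 7.6.5 treats a condition present at consent as medical history and then adds: "However, if the study subject's condition deteriorates after the consent signature, it will be recorded as an AE". The section closes with a rule for the disease under study: "Worsening of atopic dermatitis is captured by efficacy assessments and will not be recorded as an AE". That rule is not limited to non-serious worsening, and neither document limits it elsewhere.

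Protocol 7.6.3 reads: "A serious adverse event or reaction is any untoward medical occurrence that, at any dose has any of the following consequences". One listed consequence is "Requires in-patient hospitalization or prolongation of existing hospitalization". AD is not excluded.

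Protocol 7.6.7 requires every SAE, related or not, to be sent in within 24 hours, and explains in brackets: "this refers to any AE that meets one or more of the aforementioned serious criteria". Whether an event needs expedited reporting to authorities is decided for the SAEs received. On the period covered it says: "The SAE reporting period ends at the end of the follow-up period or if the subject begins an alternative therapy".

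For analysis, protocol 8.3.3 states that "SAEs will be tabulated by treatment group, relationship to the test article". SAP 13.1 summarises serious treatment-emergent events by system organ class and preferred term. The one planned safety output on AD worsening is the proportion of subjects who withdraw because of it, at Weeks 2, 4, 8 and 12 (protocol section 3, SAP 13.1).

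**The concern.** Leaving routine, non-serious worsening of the disease under study to the efficacy measures is a defensible choice. The difficulty is with worsening that meets a seriousness criterion. The reason 7.6.5 gives is that efficacy assessments already capture worsening. They do capture how bad the skin is, but not whether the subject was admitted or was in danger.

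What is at stake is the completeness of the serious-event record: the 24-hour report, the decision on expedited reporting, the data the DSMB uses when it compares arms unblinded, and the final SAE tables. With about 50 centers in three countries, an instruction that can be read two ways also invites handling that differs by site.

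**Working it through.** There is no figure to reproduce, because the point rests on text. The check follows one hypothetical event, a subject admitted to hospital for an AD flare during the study, under each of the two readings.

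| Step | Site follows 7.6.5 | Site follows 7.6.3 |
|---|---|---|
| Recorded as an AE | No | Yes |
| SAE form within 24 hours (7.6.7) | No: the bracket requires an AE first | Yes |
| Review for expedited reporting (7.6.7) | None: no SAE is received | Done |
| SAE data available to the DSMB (4.5) | Absent | Present |
| SAE tables (8.3.3) and serious-TEAE tables (SAP 13.1) | Absent: no rule adds events from efficacy data | Present, if treatment-emergent for SAP 13.1 |

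Both columns follow from the current text, and no sentence ranks one section above the other.

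The next question is whether another route catches the event in the left-hand column.

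1. **Efficacy scales (7.1.1 to 7.1.4).** EASI, IGA, SCORAD and BSA have no field for an admission or a threat to life. After Week 4 the scheduled visits are 4 weeks apart (Weeks 4, 8, 12 and 16). The daily pruritus NRS (7.1.5) records itch only.
2. **Handling of rescue (SAP 6.2).** Efficacy data after the start of prohibited medication are set to missing. A flare bad enough to need such treatment therefore leaves the main efficacy analyses from that point. One sensitivity analysis brings the data back, for EASI only.
3. **Withdrawal for worsening AD (SAP 13.1).** This counts withdrawals. A subject admitted who stays in the study is not counted, and one who withdraws is not marked as serious.
4. **Medical monitor contact (6.4.2).** This is triggered by a request to use a prohibited therapy, and it is not an SAE report.
5. **Duty to alert the sponsor to unusual events (7.6.6).** This is general and names neither AD nor seriousness.

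None of the five produces an SAE record.

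Finally, the reporting period. Section 7.6.1 collects AEs and SAEs up to the final visit or contact, but 7.6.7 ends SAE reporting once an alternative therapy begins, and it does not define that term. Section 6.4.2 keeps some subjects in the study after they start a prohibited treatment for AD. If that treatment counts as an alternative therapy, a flare that becomes serious afterwards could fall outside reporting even with 7.6.5 amended.

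**The case against.** The strongest reply is that 7.6.3 already settles the matter. A flare that leads to admission is an untoward medical occurrence with a listed consequence, 7.6.7 asks for all SAEs, and an investigator who starts from the definition would file the form. This has force. A reader might infer from 7.6.5 that a serious flare is not an SAE at all, or that none would ever be reported. The documents do not support that, because 7.6.3 does not exclude AD. They support possible omission and inconsistency, not a reporting rate of zero.

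Other inferences also go too far:

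- **That 7.6.5 contradicts its own rule on deteriorating conditions.** The AD sentence is better read as a specific exception to that general rule. The conflict that matters is between 7.6.3 on one side and 7.6.5 with 7.6.7 on the other.
- **That a flare after stopping study product is serious for that reason.** Stopping is not a criterion in 7.6.3. Only a flare with a listed consequence, or one judged an important medical event, is in question.
- **That the number of missed events can be estimated.** An assumed admission rate of 0.5% to 2% of 220 subjects would give 0.005 × 220 = 1.1 to 0.02 × 220 = 4.4 subjects, but neither document supports that rate. Eligibility points to low numbers: inclusion 3 requires no significant flare for at least 4 weeks before screening, and exclusion 9 removes unstable or refractory disease with frequent hospitalizations. Exclusion 9 removes only frequent admissions, so the number need not be zero.
- **That the omission favors ASN002.** If the drug works as the sample-size section assumes (EASI change of -15 against -8), flares would be expected mainly on placebo, and their loss would not flatter the drug. Flares after stopping active drug could act the other way.

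The partial safeguards narrow the gap. A complication with its own diagnosis, such as an infection, is still an AE. Safety analyses are descriptive (8.3.3), so no formal test is affected. What stands is that the documents leave open whether a serious AD flare is to be reported.

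**Conclusion.** The point holds as an unresolved conflict between 7.6.3, 7.6.5 and 7.6.7. A site that follows 7.6.5 to the letter sends no SAE report for a serious AD flare, a site that follows 7.6.3 does, and both can claim to follow the protocol. The consequence is an SAE record that may be incomplete or inconsistent between sites. Its size cannot be stated: the documents give no rate of serious AD worsening, and the direction of any difference between arms is uncertain.

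The conclusion assumes that no instruction outside these two documents, such as a site manual, restores serious flares to SAE reporting. It is shown for protocol Version 3.0. SAP section 1 says German sites follow Version 2.2, which was not available here. Because serious safety events could be lost and the repair is small, the change should be made.

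**What to change.** 1. In protocol 7.6.5, extend the sentence on worsening AD with: *unless it meets a seriousness criterion in 7.6.3, in which case it is recorded and reported as an AE/SAE*. This reconciles 7.6.5 with 7.6.3 and lets the event enter 7.6.7. Non-serious worsening stays with the efficacy measures.
2. In protocol 7.6.7, check the clause that ends SAE reporting when an alternative therapy begins. Say whether treatment for an AD flare counts as such a therapy, and reconcile the clause with the collection period in 7.6.1 so that serious flares are not dropped again.
3. In SAP 13.1, show serious AD worsening on its own line by treatment group, so that SAE rates can be read with and without it.
4. Make the same check in the German protocol version.

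The cost is one sentence in 7.6.5, a clarification in 7.6.7 if the check shows it is needed, a notice to sites and one table line. The downside is a few more SAE forms, possibly more on placebo. The change concerns recording and reporting only and leaves the treatment of subjects as it is.
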